Project summary

Type 1 diabetes (T1D) is a chronic disease which requires daily calculations of food intake and insulin dose adjustment to achieve good glycaemic control and minimise the risk of developing diabetic complications. However, even when glycaemic control appears to be good, as demonstrated by average glycated haemoglobin (HbA1c), children and young people with T1D frequently experience glucose variability, with levels above and below the target range. The main cause of diurnal glucose variability is food intake, which can cause postprandial hyperglycaemia. Postprandial hyperglycemia can occur after any meal, although there is some evidence that it may be worse after breakfast. There is limited data on the occurrence and cause of this and its association with different variables, including food composition and the glycaemic load of a meal.

Methods:

This project will be a quantitative study. The study proposes to recruit 90 children and young people who have T1D and who regularly use Dexcom continuous glucose monitoring (CGM). Recruitment will be via their managing dietitian. The dietitian will be asked to provide baseline information about the participants which will include demographic data and information on clinical data, treatment and anthropometrics. Participants will be asked to provide access to Dexcom CGM data throughout the period of recording. Participants will be asked to test three breakfast meals (high glycaemic load, high glycaemic with 10g added protein and medium glycaemic load) plus a control meal (usual breakfast), repeating each meal twice in a randomized order using a Latin square randomisation. The dietitian will be asked to optimise the participants insulin doses prior to commencing test meals. Participants will be asked to complete a questionnaire for each of the postprandial test and control meal periods. This will include questions about their diabetes management, food and fluid intake in addition to questions on activities all of which took place during the three-hour postprandial period. The glycaemic response to the test and control meals will be analysed using the CGM data and the results statistically described using univariate, bivariate and multivariate analysis.

Study protocol

Full Study Title:

The Breakfast Rise, Education and Knowledge Study in Children and Young People who have Type 1 Diabetes (T1D): The BREAK study.

Short title

The BREAK study.

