Although the addition of a moderate amount of protein to a carbohydrate containing meal is recommended in international guidelines (Smart *et al.* 2018) there appears to be no evidence for this as a prevention of postprandial hyperglycaemia at breakfast. It is agreed that further research into the dietetic management of T1D is required (Smart *et al.* 2018). There is also a dearth of evidence on prevalence and management of postprandial hyperglycaemia after breakfast. Seven studies tested meals at breakfast time (Ryan *et al.* 2008; Smart *et al.* 2012; Smart *et al.* 2013; Piechowiak *et al.* 2017; Faber *et al.* 2017; Lopez *et al.* 2018) however none of the aims of these studies were to establish prevalence nor resolution of postprandial hyperglycaemia at breakfast. Only two considered diet quality at breakfast (Ryan *et al.* 2008;

Groele *et al.* 2014) and neither of these provided any evidence of how to manage postprandial hyperglycaemia after breakfast.

Conclusion

It is known that chronic hyperglycaemia causes increased risk of diabetic complications. It is possible that both glucose variability and postprandial hyperglycaemia are independent risk factors for this as well. There is some evidence that glucose variability and postprandial hyperglycaemic are common occurrence for children who have T1D. However, there is a paucity of published data on the prevalence of postprandial hyperglycaemia after breakfast in children and young people with T1D and limited evidence for the impact of glycaemic load and manipulation with protein. The need for closer examination of postprandial glucose variability to elucidate methods to reduce this, has been highlighted (Tansey *et al.* 2016). Although this applies to all meals, focusing on minimising postprandial hyperglycaemia after breakfast is paramount. This can help ensure good control through the morning and rest of the day when children are at school and actively learning (Tansey *et al.* 2016).

Aim:

To describe the distribution and dispersion of glucose variability and postprandial hyperglycaemia following test and control meals at breakfast, in children and young people with T1D, using measurements from Dexcom CGM.

Objectives:

- To determine the glucose variability diurnally, nocturnally and in the three-hour postprandial breakfast test meal period using measurement of 'time in range', 'time above range' and 'time below range'.

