- To determine the variability of glucose excursion, level and peak and the recovery time in the three-hour postprandial period.
- To describe comparisons between all the above measurements and the variables of sex, age, disease duration, BMI, HbA1c, insulin dose/sensitivity and insulin regimen.
- To describe comparisons between all the above measurements and the glycaemic load and composition of the test and control meals.

Study design

This is a quantitative study. Dexcom CGM data will be collected for the period of recording. Participants will be asked to test three breakfast meals on two occasions and submit a postprandial questionnaire after each test meal to confirm it has been tested. The postprandial period will be three hours following the end of the breakfast test meal. The test meal recipes

will be provided by the chief investigator. The dietary composition of the meals has been analysed using the Nutritics dietary analysis programme (Nutritics, 2022). The glycaemic index and load of the meals is estimated from the Nutritics programme which uses available data from the international tables of glycaemic index and glycaemic loads (Atkinson *et al.* 2008; 2021). Most foods were based on average composition across different brands. For the added fibre bread used in test meal 3, an average of three known brands was used calculated by the chief investigator. The meals will be taken in the home environment with the food provided by the families. The participants will be asked to take the test meal on a day when their CGM reading is between 4-10mmol/l and when there has been no nocturnal hypoglycaemia on the night before the planned test. The participants will act as their own control. They will be asked to complete a postprandial questionnaire for control meals as well. The control meals will be their usual breakfast of choice. The study duration, commencing with the recruitment of the first participant and ending when data has been fully described, is anticipated to be two years.

Participants

Eligibility criteria

- Children and young people aged between 5-17 years
- Diagnosis of type 1 diabetes for a minimum of one year
- On multiple daily injections (MDI) together with carbohydrate counting or Continuous Subcutaneous Insulin Infusion (CSII) using either open or closed loop systems.
- Use Dexcom continuous glucose monitoring (CGM) on a regular basis
- Have a Dexcom Clarity account and use the Clarity App

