- Current insulin regimen - including the type of insulin prescribed and if applicable type of insulin pump i.e. open or closed loop system.

Run-in period

At recruitment the dietitians will be asked to arrange a review of the participants insulin regimen including the insulin to carbohydrate ratio's (ICR), insulin sensitivity factor (ISF) and basal background insulin doses/rates. The dietitian will be asked to inform the chief investigator when this has taken place. Participants will be asked to commence the test meals following this.

Glucose measurement

Data on interstitial glucose will be collected via Dexcom CGM. The Dexcom CGM data will be accessed by an NHS Highland research 'Clarity Clinic' with Dexcom CLARITY® Clinic Portal (Dexcom In, San Diego, CA, USA). The chief investigator is administrator of this clinic. Once the managing dietitian has obtained each participant's consent, the participant's parent's email address will be sent to the chief investigator along with the baseline information/data as described above. The chief investigator, as administrator of the Clarity Clinic account, will then invite the participant, via email, to be added to the clinic. Once the invite has been accepted, it will stand for the period of the recording i.e. until all the test meals and questionnaires have been completed. Once the participant has submitted their last questionnaire, they will be removed from the Dexcom CLARITY® Clinic Portal. They will be removed from the clinic portal if they withdraw from the study.

Test and control meals

Following the provision of CGM data and review of the insulin regimen by the diabetes team, participants will be randomised to test each of the three test meals on two separate occasions with a control meal (usual breakfast meal) for each test meal. Randomisation will be achieved using a Latin square randomisation. The tool used for this will be <http://www.jerrydallal.com/random/randomize.htm>. Randomisation will be done in a block of four.

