- Mean glucose
- Glucose variability (GV) % coefficient of variation (COV) target $\leq 36\%$
- Time in range (TIR) % and time spent between 3.9-10mmol/l
- Time above target (TAR) % and time spent $>10.1\text{-}<13.9\text{mmol/l}$ and $>13.9\text{mmol/l}$
- Time below range (TBR) % and time spent 3.0-3.8mmol/l and $<3\text{mmol/l}$

Target glucose levels:

- TIR - % of readings $>70\%$ or 16hr 48min
- TAR - % of readings $<25\%$ or $<6\text{hr}$ high and $<5\%$ 1hr 12min very high
- TBR- % of readings $<4\%$ or $<1\text{hr}$ low and $<1\%$ or $<15\text{min}$ very low

Primary outcome measure:

- Mean glucose (mmol/l) in the three-hour postprandial breakfast period calculated from the CGM measurements at 5 minutes intervals.

Secondary outcome measures – post prandial period:

- Number and percentage who had pre-prandial glucose in target, mean peak glucose level (mmol/l), mean time to peak (mins), mean time to recover (to pre-prandial levels) (mins) in the three-hour postprandial breakfast period
- TIR, TBR and TAR (% and time) in the three-hour postprandial breakfast period
- Comparisons of the above measurements between cohorts and breakfast test meal compositions.

Data analysis

This will be a mix of univariate, bivariate and multivariate analysis as this is best suited to describing, summarising and visualising these data. Outputs will include the distribution of glucose levels post-breakfast to determine the spread and dispersion of the data.

Safety considerations

Recruitment/consent

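### The four-meal comparison of absolute three-hour mean glucose is planned without adjustment for pre-meal glucose, although test meals may start anywhere from 4 to 10 mmol/l and CGM records the value

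*Combined protocol and SAP*

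**What the plan says.** All references are to the combined protocol and SAP.

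- **Primary outcome measure:** "Mean glucose (mmol/l) in the three-hour postprandial breakfast period calculated from the CGM measurements at 5 minutes intervals". No contrast is attached to it. Comparisons between meals are listed under the secondary outcomes.
- **Study design, starting level:** "The participants will be asked to take the test meal on a day when their CGM reading is between 4-10mmol/l". Days that follow nocturnal hypoglycaemia are also avoided.
- **Study design, outcome window:** "The postprandial period will be three hours following the end of the breakfast test meal". The first value in the window is therefore not a pre-meal value.
- **Project summary:** the three test meals "plus a control meal (usual breakfast), repeating each meal twice in a randomized order using a Latin square randomisation". The section on test and control meals puts the control differently: participants will "test each of the three test meals on two separate occasions with a control meal (usual breakfast meal) for each test meal".
- **Sample size:** a within-factors repeated-measures ANOVA over the three test meals and control, with effect size f = 0.15, alpha 0.05, power 0.80 and correlation 0.5, giving 64. No covariate is named.
- **Data analysis:** univariate, bivariate and multivariate methods in general terms, with no model, primary contrast or covariate.

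Pre-meal glucose appears as a condition on the test day and, among the secondary outcomes, as the proportion in target and the reference for recovery time. It may also enter through the objective "To determine the variability of glucose excursion, level and peak and the recovery time in the three-hour postprandial period", but excursion is not defined there and is not in the outcome list. The variables named for comparison are in "To describe comparisons between all the above measurements and the variables of sex, age, disease duration, BMI, HbA1c, insulin dose/sensitivity and insulin regimen". These are child characteristics, and pre-meal glucose is not one of them. No section says which CGM reading counts as pre-prandial.

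**The concern.** An absolute three-hour mean can carry over the level from which the child started. With an allowed starting range 6 mmol/l wide, part of the spread between one child's occasions may reflect the start rather than the meal. Adjustment for a value measured before eating removes that part.

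Three things are at stake:

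- **Precision.** Meal differences may have wider intervals than the data require.
- **Chance imbalance.** Even with randomised order, mean starting glucose can differ between meals by luck, and an unadjusted comparison does not correct for it.
- **Choice after the data are seen.** Raw, excursion-type and adjusted comparisons all fit the present wording, and so do several definitions of the pre-meal reading.

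**Working it through.** **Step 1. Reproduce the plan's figure.** Inputs from the Sample size section: f = 0.15, m = 4 measurements, correlation 0.5, alpha 0.05. Sphericity is assumed.

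λ = f² × N × m / (1 − ρ), with 3 and 3(N − 1) degrees of freedom.

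The smallest N with power of at least 0.80 is 62 (power 0.801). Rounding up to a multiple of four groups gives 64, the stated figure. At N = 64, λ = 0.0225 × 64 × 4 / 0.5 = 5.76 / 0.5 = 11.52, and power is 0.815 on 3 and 189 degrees of freedom. The plan's number is sound on its own terms.

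**Step 2. Add the covariate.** These quantities are assumed, because the documents do not give them:

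- r, the within-child, occasion-level correlation between pre-meal glucose and the three-hour mean: 0.1, 0.3 and 0.5.
- s, the child-by-meal share of the within-child variance: 0 and 0.5. Averaging repeat occasions does not reduce this share.
- f and the correlation of 0.5 describe single occasions.

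λ = 5.76 / V, with 188 denominator degrees of freedom after adjustment.

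- One occasion per meal: V = 0.5(1 − r²).
- Two occasions per meal, as in the Project summary: V = 0.5[s + (1 − s)(1 − r²)/2]. Setting r = 0 gives the unadjusted case.

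The interval for a difference between two meals narrows by 1 − √(V adjusted / V unadjusted).

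| Case | r | V | λ | Power | CI narrower by |
|---|---|---|---|---|---|
| One occasion | unadjusted | 0.500 | 11.52 | 0.815 | – |
| | 0.1 | 0.495 | 11.64 | 0.819 | 0.5% |
| | 0.3 | 0.455 | 12.66 | 0.853 | 4.6% |
| | 0.5 | 0.375 | 15.36 | 0.918 | 13.4% |
| Two occasions, s = 0 | unadjusted | 0.250 | 23.04 | 0.987 | – |
| | 0.1 | 0.2475 | 23.27 | 0.988 | 0.5% |
| | 0.3 | 0.2275 | 25.32 | 0.993 | 4.6% |
| | 0.5 | 0.1875 | 30.72 | 0.998 | 13.4% |
| Two occasions, s = 0.5 | unadjusted | 0.375 | 15.36 | 0.918 | – |
| | 0.1 | 0.37375 | 15.41 | 0.919 | 0.2% |
| | 0.3 | 0.36375 | 15.84 | 0.926 | 1.5% |
| | 0.5 | 0.34375 | 16.76 | 0.940 | 4.3% |

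The one-occasion rows show how the gain works. The two-occasion rows match the design. A simulation of 4,000 trials per case agreed to about one point; for s = 0.5 and r = 0.5 it gave 0.908 unadjusted and 0.929 adjusted.

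**Step 3. Size of a chance imbalance.** Suppose starting values are uniform over 4 to 10 mmol/l (SD = 6/√12 = 1.73) and independent between meals. Then 95% of differences in mean starting glucose between two meals at N = 64 lie within:

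- one occasion: ±1.96 × 1.73 × √(2/64) = ±0.60 mmol/l;
- two occasions: ±1.96 × 1.73 × √(2/128) = ±0.42 mmol/l.

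How much of this reaches the three-hour mean depends on a slope that the documents do not give. For assumed slopes of 0.25 to 1.0, the two-occasion shift is at most about 0.11 to 0.42 mmol/l. With an assumed SD of 1.0, the two-occasion imbalance is ±0.25 mmol/l.

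**The case against.** The strongest reply has four parts.

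**The plan names no primary meal contrast.** The aim is descriptive and meal comparisons are secondary. This stands as a limit on the wording: the contrast is inferred from the ANOVA behind the sample size, the randomised meal order and the stated hope of evidence on glycaemic load and added protein. The inference is reasonable, but the plan does not say it.

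**The gain is small.** This stands for power, which is already 0.918 to 0.987 with two occasions under the stated assumptions. Usual insulin dosing and closed-loop use could also make r small. Power close to its ceiling does, however, understate the value for a study that aims to describe, where interval width matters.

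**The plan already handles starting glucose.** It restricts the start and would compare the proportion in target between meals. That would expose a coarse imbalance but would not correct the outcome for it. Multivariate analysis could include pre-meal glucose, but nothing commits to it.

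**The covariate needs care.** This stands. Children keep their usual dose timing, so a reading just before eating may already reflect insulin given for that meal. Raw pre-meal glucose would mix within-child and between-child slopes. A pre-meal reading also needs a start time, and the questionnaire appendix was not available.

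A reader might go further and infer that test-versus-control contrasts are biased because the 4 to 10 condition is worded for the test meal only. The documents do not support this. An objective refers to measurement "in the three-hour postprandial breakfast test meal period", so the term is used loosely for the outcome window. The Project summary places the control meal in the randomised order, and the meal instructions in the appendix may settle the matter.

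**Conclusion.** The point holds as one of precision and prespecification. The comparison implied by the sample size uses an absolute mean, allows a 6 mmol/l range of starting values for test meals, and leaves a recorded covariate unused.

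No bias is shown. Among the test meals, randomised order and a common starting condition leave noise and chance imbalance only. No bias figure is claimed for test versus control.

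For assumed r of 0.1 to 0.5 and two occasions per meal, power rises by about 0 to 2 points. The interval for a meal difference narrows by 0.5% to 13.4% with no child-by-meal variance, and by 0.2% to 4.3% if that variance is half the within-child total. If r is near zero the gain is almost nil. It would also be wrong to conclude that 64 is too few because adjustment is missing, since the figure reproduces without it.

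The change is worth making because it costs little and closes a choice now open after the data are seen. Confidence is medium: the omission is clear, but its size is not.

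**What to change.** In the Data analysis section:

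1. Name the meal comparison of three-hour mean glucose, and analyse it with a mixed model that uses both occasions of each meal.
2. Adjust for occasion-specific pre-meal glucose, entered as two terms: the child's mean over all occasions, and each occasion's deviation from that mean.
3. Define pre-meal glucose in advance as one fixed CGM reading before the meal, taken before any pre-meal bolus where the recorded times allow.
4. Report the unadjusted comparison as supporting.

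Separately, state whether the 4 to 10 mmol/l condition covers control meals. The point does not depend on the answer.

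**Cost.** SAP wording and standard software, with no further glucose data. The outcome window runs from the end of the meal, so the team should confirm that the questionnaire records the start time; if it does not, an item is needed.

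**Downside.** The model assumes a roughly linear relation with starting glucose and a common slope, which may not hold across insulin regimens. The supporting unadjusted analysis shows how far the result depends on it.

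### For test meals, the secondary outcome of pre-prandial glucose in target is largely decided by the request to take those meals when CGM reads 4-10 mmol/l

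*Combined protocol and SAP*

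**What the plan says.** Under Outcome measures, the secondary list for the postprandial period opens with "Number and percentage who had pre-prandial glucose in target". Its last item says that the listed measurements will be compared between cohorts and between test-meal compositions. No target is given for the pre-prandial reading. The only in-range band in that section is "Time in range (TIR) % and time spent between 3.9-10mmol/l".

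Study design sets two conditions for the day of a test meal. One concerns the glucose level: "The participants will be asked to take the test meal on a day when their CGM reading is between 4-10mmol/l". The other looks back to the hours of sleep and asks for "no nocturnal hypoglycaemia on the night before the planned test". Both are requests to families eating at home, and both are worded for test meals. For controls, the same section says only "The control meals will be their usual breakfast of choice"; neither condition is repeated for them.

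The first item under Objectives is "To determine the glucose variability diurnally, nocturnally and in the three-hour postprandial breakfast test meal period", using time in, above and below range. Study design and Glucose measurement collect CGM over the whole recording period, up to the last questionnaire. Creation of new data and Definition of end of study are narrower: they speak of CGM when meals are tested and of exporting the data for the meal period.

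**The concern.** An outcome should be free to vary with what it is meant to describe. Here the day of a test meal is chosen on nearly the same quantity that is then reported as a result. A child who often wakes above 10 mmol/l and a child who rarely does will both, if they follow the instructions, contribute test mornings that begin in range.

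Two misreadings could follow. A high in-target percentage could be taken as a description of usual pre-breakfast control. A lack of difference by HbA1c, age, regimen or meal could be taken as a clinical finding, when the selection of days would produce it whatever the truth. The protocol does not comment on either. If control mornings are unrestricted, setting them beside test mornings, or pooling the two, adds a difference that comes from the day rule.

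**Working it through.** The plan attaches no figure to this outcome. Its one computed figure, the sample size of 64, concerns the repeated-measures ANOVA and plays no part here. It does reproduce: f = 0.15, alpha 0.05, power 0.80, correlation 0.5 and four measurements give N = 62, or 64 when rounded up to a multiple of four groups, with power 0.81.

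**1. Interval check.** The start condition is 4-10 mmol/l (Study design). The in-range band is 3.9-10 mmol/l (Outcome measures). Every value in the first lies in the second. If target means this band, and the reading in the request is the pre-meal one, each adherent test morning counts as in target: 100%.

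**2. Partial adherence.** Let *a* be the share of test meals that follow the condition, and *p* the in-target rate on unrestricted mornings. The test-meal figure is a + (1 - a)p. The documents give neither input, so both are assumed: *a* = 0.80-0.90, *p* = 0.30-0.90.
- Lowest: 0.80 + 0.20 × 0.30 = 0.86.
- Highest: 0.90 + 0.10 × 0.90 = 0.99.

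**3. Effect on comparisons.** With equal adherence, a true difference p1 - p2 between two cohorts shrinks to (1 - a)(p1 - p2). At *a* = 0.90, a true gap of 0.90 - 0.50 = 40 points appears as 0.10 × 40 = 4 points. Conversely, two cohorts with the same *p* = 0.50 but adherence of 1.00 and 0.80 show 100% and 0.80 + 0.20 × 0.50 = 90%, a 10-point gap due to adherence alone.

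**4. Control mornings.** With six test meals at full adherence and unrestricted controls, the pooled figure is (6 × 1 + c × p)/(6 + c), where *c* is the number of control meals. The Project summary implies *c* = 2; Test and control meals can be read as up to 6.
- c = 2: (6 + 0.6)/8 = 82.5% to (6 + 1.8)/8 = 97.5%.
- c = 6: (6 + 1.8)/12 = 65% to (6 + 5.4)/12 = 95%.

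The pooled value depends on the mix of meals as well as on the children.

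**5. A narrower target.** For any target inside 4-10, the rate on adherent mornings is P(target)/P(4-10), which is at least P(target). As an illustration only, take 4-7 mmol/l and lognormal waking glucose, with σ² = ln(1 + (SD/mean)²) and μ = ln(mean) - σ²/2. Target, means and SDs are all assumed.

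| Mean, SD (mmol/l) | All mornings | Mornings within 4-10 |
|---|---|---|
| 8, 3 | 38% | 52% |
| 9, 3 | 26% | 39% |
| 10, 3.5 | 18% | 33% |

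The outcome is no longer constant, but it is raised by the selection.

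**6. Nights.** The night condition covers the night before each test meal, so six nights. As a share of an assumed recording of 14, 28 or 56 days this is 6/14 = 43%, 6/28 = 21% or 6/56 = 11%. The other nights are unrestricted.

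**The case against.** The strongest reply is that the condition is a request, followed unsupervised at home, and is worded as a day on which CGM reads 4-10, without tying the reading to the first mouthful. Counting how many meals began in target is then a sensible baseline and compliance description. This stands, and it is the reason to keep the figure under an adherence label. It does not support comparing the figure between cohorts or meals as an outcome.

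It can also be said that the pre-prandial target is undefined, so a fixed 100% is only one reading. That is correct. Under a narrower target the figure varies, though it is still selected upward. Control mornings may also vary freely. That keeps some information in the data, but the planned meal-composition comparison names the test meals, where the selection operates.

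Finally, no objective asks how often children wake in target, the item is secondary, and it does not enter the sample size. This limits the consequences, but the outcome is still listed for comparison.

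A reader might go further and infer that the night condition fixes nocturnal time below range near zero. The documents do not support that. CGM is collected over the whole recording period and the condition touches only nights before test meals. Near-zero values would follow only if those nights alone were analysed, and no section says so. What remains is that the plan does not state which nights count, while two sections use narrower wording about the data.

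**Conclusion.** The point holds for test meals. If target means 3.9-10 mmol/l and the request refers to the pre-meal reading, the outcome is 100% with full adherence and 86-99% under the assumed adherence and in-target rates; what variation is left mainly reflects adherence. With a narrower target it is biased upward: in the illustration, 33-52% against 18-38%. Either way, the planned comparison across cohorts and test-meal compositions cannot show how often these children start breakfast in target.

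The interval check rests on the documents alone. Adherence, in-target rates, the glucose distribution, the 4-7 range and the recording length are assumptions. A reader might infer that the study cannot describe pre-breakfast or nocturnal glucose in these children at all. That is too strong, since control mornings are not stated to be restricted and whole-period CGM contains unselected mornings and nights. Nor do the documents give a basis for stating by how many points the test-day figure would overstate usual control.

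**What to change.** In Outcome measures:
- Define the pre-prandial target and the reading it applies to.
- Report the test-day figure as adherence to the start condition, separately from control mornings.
- Remove it from the between-cohort and between-meal comparisons.

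If usual pre-breakfast control is to be described, take it from all mornings in the recording period using a stated clock window. Align the export wording in Definition of end of study with the whole-period collection in Study design and Glucose measurement. This should be settled before export begins: participants leave the portal after their last questionnaire, and Destruction of data says the Clarity clinic holds CGM for only three months, so mornings not exported may be lost to the study.

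As a clarification only, state that the diurnal and nocturnal metrics of the first objective use all recorded days and nights.

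The cost is revised wording, a possibly wider export, extra CGM processing, and an approximate breakfast time on non-study mornings. No change to the start conditions is proposed.
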